4.2.6.1 Other subject reported outcome variables

Total rescue medication use

Total rescue medication use and the number of nights with awakening and their change from baseline will be summarised by treatment and visit for subjects in the FAS.

Change from baseline in total rescue medication use will be analysed using the same MMRM method for pre-dose/pre-BD FEV₁ (L) as described in Section 4.2.5.5. Results will be presented in terms of LSMEANS (with the OBSMARGIN option added), treatment differences in LSMEANS, 95% CI, and p-values for all visits.

Nights with awakening due to respiratory symptoms

The number of nights with awakening and change from baseline will be summarised by treatment and visit.

Change from baseline in the proportion of nights with awakening due to COPD awakening will be analysed using the same MMRM method for pre-dose/pre-BD FEV₁ (L) as described in Section 4.2.5.5. Results will be presented in terms of LSMEANS (with the OBSMARGIN option added), treatment differences in LSMEANS, 95% CI, and p-values for all visits.

4.2.6.2 Biomarkers

Biomarker serum TSLP results and plasma Fibrinogen results and changes from baseline will be summarised by treatment and visit.

Other biomarkers and the results of any investigation will be reported separately in a scientific report or publication and analyses covered by a separate SAP.

4.2.6.3 Genetic (DNA) sampling

The results of any investigation will be reported separately in a scientific report or publication and analyses covered by a separate SAP.

4.2.7 Safety and tolerability

All safety variables will be summarised using the safety analysis set (see Section 2.1.2 for details).

4.2.7.1 Adverse events

AEs will be summarised separately for the on-treatment and on-study periods, as defined in Section 3.1.4 unless stated otherwise. All AE summaries will be presented by treatment group. AEs occurring

during the screening/run-in period, or occurring post-treatment will be listed, but not summarised separately.

An overall summary table will be produced showing the number and percentage of subjects with at least one AE in each of the following categories: any AEs, SAEs, AEs with a fatal outcome, and AEs leading to discontinuation of IP (DAEs). The total number of AEs in the different AE categories will also be presented as well as the number of subjects (i.e. accounting for multiple occurrences of the same event in a subject).

All AEs will be summarised by SOC and PT assigned to the event using the MedDRA dictionary. For each PT, the number and percentage of subjects reporting at least one occurrence of the event will be presented (i.e. subjects with multiple occurrences of the same PT will only be counted once).

Similar summaries by SOC and PT will also be presented for:

- SAEs
- AEs with a fatal outcome
- DAEs
- DAEs casually related to IP
- SAEs leading to discontinuation of IP
- Each AESI category separately
- The most common AEs (defined as those occurring in >3% of subjects in either treatment group) by PT only

All AEs (by PT) will be summarised additionally by causality and maximum intensity. If a subject reports multiple occurrences within each PT, the maximum intensity will be taken as the highest recorded (the order being mild, moderate, and severe) respectively.

Separate listings of subjects with AEs, SAEs, AEs with a fatal outcome, DAEs, SAEs leading to discontinuation of IP, and severe infections will be presented.

Exposure-adjusted AE summaries will be presented by SOC and PT for each of the following (on-treatment summaries only):

- All AEs
- SAEs

- Each AESI separately

In these summaries, the exposure-adjusted rate will be defined for each treatment as the number of subjects in that treatment group reporting the AE divided by the total time at risk for all subjects in that treatment group, the latter as defined in Section 3.3.2. Rates will be reported as events per 100 subject-years.

Events confirmed by the independent adjudication committee (major adverse cardiac events (MACE) and malignancies) will be summarised by treatment group.

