9.4.3.2 Adverse Events

Adverse events experienced by the subjects will be collected throughout the entire study and will be coded by the AstraZeneca designee using the latest version of the Medical Dictionary for Regulatory Activities (MedDRA).

Adverse event data will be categorized according to their onset date into the following study periods:

- AEs occurring during screening (onset date ≥ Visit 1 and before the first dose of study treatment)
- AEs occurring during treatment (onset date \geq the first day of study treatment and \leq the last day of study treatment + 4 weeks)
- AEs occurring during follow-up
 - (onset date > the last day of study treatment + 4 weeks and ≤ the last day of study treatment + 16 weeks)

The timing of AEs will be assigned to the period in which they first occurred. If an AE has a missing onset date, then unless the stop date of the AE indicates otherwise, this will be considered an on-treatment event. Similarly, if an AE has a partial onset date, then unless the partial onset date or the stop date indicates otherwise, this will be considered an on-treatment AE.

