9.5.4 Safety Analyses

AEs will be summarized by means of counts and exposure adjusted rate summaries by study period (treatment period and follow-up period). AEs will be listed for each subject and summarized by System Organ Class (SOC) and Preferred Term (PT) assigned to the event by MedDRA. Laboratory safety variables will be summarized using standard summary statistics and plots as appropriate. Other safety variables will be summarized as appropriate. Further details will be provided in the SAP.

Laboratory data for hematology and clinical chemistry will be summarized. The frequency of changes with respect to normal ranges between baseline and each post-treatment time point will be tabulated. Frequencies of clinically noteworthy values (defined in the SAP) occurring during the clinical study will also be given. Shifts from normal to abnormal between baseline and each post-baseline time point will be evaluated for urinalysis. Changes in vital signs and ECGs will be examined at each visit and at endpoint. Frequencies of clinically noteworthy values (defined in the SAP) occurring during the clinical study will be presented. Shifts from normal to abnormal between baseline and follow-up will be evaluated for the physical examination.

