3.3.2 Adverse events (AEs) - general

AEs experienced by any subject at any time during the entire study will be coded using the latest version of the Medical Dictionary for Regulatory Activities (MedDRA).

AEs will be separated according to their onset date into the following study periods:

- AEs occurring during screening/run-in period: date of Visit 1 \leq AE onset date $<$ date of first dose of IP
- AEs occurring during on-treatment period: date of first dose of IP \leq AE onset date \leq minimum (date of last dose of IP + 33 days, date of death, date of study withdrawal)
- AEs occurring during post-treatment period (for subjects still being followed up then): date of last dose of IP + 33 days $<$ AE onset date \leq study completion or withdrawal date
- AEs occurring during on-study period: date of first dose of IP \leq AE onset date \leq study completion or withdrawal date

AEs occurring during screening run-in period will be listed only.

If the AE has a completely missing (and unresolvable) onset date, then the AE will be assumed to be treatment-emergent, unless the end date indicates unambiguously that the AE resolved before treatment started. If the AE has a partially missing (and unresolvable) onset date, then the AE will also be assumed to be treatment-emergent, unless either the end date indicates unambiguously that the AE resolved before treatment started, or the partial onset date is in the month/year prior to start of treatment.

For exposure-adjusted summaries of specific AEs, the time at risk for each subject will be derived as the time during the relevant period for analysis during which the subject had no occurrence of that AE. Specifically, for on-treatment AEs, time at risk is defined as:

Time at risk (days) = minimum (date of last dose of IP + 33 days; date of death; date of study withdrawal; date of first adverse event occurrence) – date of first dose of IP + 1

The total time at risk (years) for a treatment group will be derived as the sum of the individual subject's times at risk (days) up to the first adverse event occurrence for that treatment group and divided by 365.25.

In all exposure-adjusted summaries of AEs, multiple occurrences of the same event for a particular subject will not be counted as separate events. A subject will either be considered to have no events of the type being summarised, or one or more occurrences of that event.

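### The SAP omits the separate follow-up-period adverse event summary that the protocol plans, and SAP Section 6 does not declare the change

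*SAP*

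**What the plan says.** - **Protocol 9.5.4 (Safety Analyses):** "AEs will be summarized by means of counts and exposure adjusted rate summaries by study period (treatment period and follow-up period". Further detail is left to the SAP.
- **Protocol 9.4.3.2 (Adverse Events):** the treatment period closes at "the last day of study treatment + 4 weeks". Follow-up AEs are those with onset after "the last day of study treatment + 4 weeks and ≤ the last day of study treatment + 16 weeks".
- **SAP 3.3.2:** on-treatment closes at "minimum (date of last dose of IP + 33 days, date of death, date of study withdrawal". The post-treatment period begins after that 33-day point and runs to study completion or withdrawal, with no 16-week limit.
- **SAP 2.1.5:** gives the reason for 33 days, which is to keep information from an IP discontinuation visit held inside its window.
- **SAP 4.2.7.1:** "AEs will be summarised separately for the on-treatment and on-study periods, as defined in Section 3.1.4 unless stated otherwise". AEs in run-in "or occurring post-treatment will be listed, but not summarised separately". The exposure-adjusted summaries (all AEs, SAEs, each AESI) are restricted to on-treatment.
- **SAP 3.1.4:** the on-study period pools planned treatment and follow-up.
- **SAP Sections 1 and 6:** Section 1 says that changes from the protocol will be described in Section 6. Section 6 says there are none.
- **SAP amendment history:** records neither difference, although it logs two other edits to the same material (the time-at-risk definition in 3.3.2 and exposure-adjusted rates for SAE tables).

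**The concern.** The protocol names two reporting periods and two statistics for each. The SAP keeps one of those periods, replaces the other with a pooled period, and drops the follow-up rate. This contradicts the protocol; it does not merely fill in detail the protocol left open.

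The follow-up visits at Weeks 58 and 64 serve immunogenicity and safety evaluation (Protocol 4.1). The protocol equates 16 weeks with 5 half-lives (Protocol 5.3), so one half-life is 16/5 = 3.2 weeks. The SAP's 33-day boundary is 33/7 = 4.7 weeks, or 4.7/3.2 ≈ 1.5 half-lives after the last dose. Follow-up therefore still includes declining exposure, and a reader may want to see those events by arm, apart from a year of on-treatment events. A reader who trusts Section 6 would also expect a table that will not be produced.

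**Working it through.** No sample size, power or alpha figure is involved. The check is a comparison of text plus day arithmetic.

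**1. Planned tables, side by side.**

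| Item | Protocol 9.5.4 | SAP 4.2.7.1 |
|---|---|---|
| Treatment-period counts | yes | yes |
| Treatment-period exposure-adjusted rates | yes | yes |
| Follow-up counts | yes | listing only |
| Follow-up exposure-adjusted rates | yes | none |
| Pooled on-study counts | not mentioned | yes |

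**2. What subtraction recovers.** By the SAP 3.3.2 definitions, on-study AEs are the on-treatment AEs plus the post-treatment AEs.

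- *Event totals.* The overall table gives total numbers of AEs by category and arm for both periods. Events add up, so post-treatment events = on-study events − on-treatment events. This works for any AE, SAEs, fatal AEs and AEs leading to discontinuation.
- *Subject counts by SOC/PT.* A subject is counted once per term. Let A be subjects with the term on-treatment only, B in both periods, and C post-treatment only. The on-treatment table shows A + B, and the on-study table shows A + B + C. The difference is C, but the follow-up count is B + C. Subtraction therefore gives a lower bound that misses B.
- *Rates.* No post-treatment time at risk is tabulated, so no follow-up rate can be formed.

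**3. Boundary for a subject dosed through Week 48.** Inputs are Week 48 = Day 337 and Week 64 = Day 449 (SAP Table 1).

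- Protocol: 337 + 28 = Day 365 closes treatment, and 337 + 112 = Day 449 closes follow-up. Length: 449 − 365 = 84 days.
- SAP: 337 + 33 = Day 370 closes on-treatment. Length to the same end: 449 − 370 = 79 days.
- Shift: 370 − 365 = 5 days. This is 5/84 = 6.0% of protocol follow-up and adds 5/365 = 1.4% to on-treatment time.
- Origin of 33: the discontinuation visit is due at 4 weeks ± 5 days (Protocol 7.1.1), and 28 + 5 = 33.
- Share of a completer's nominal on-study time with no rate of its own, under the SAP boundary: 79/449 = 17.6%.

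**4. Early discontinuer, extreme case of one dose on Day 1.** Protocol follow-up is Day 30 (1 + 28 + 1) to Day 113 (1 + 112). SAP post-treatment runs from Day 35 (1 + 33 + 1) to study completion or withdrawal. An AE after Day 113 belongs to neither protocol period, but the SAP does assign it to one.

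**The case against.** The best defence is that the on-study tables already carry the follow-up AEs. They are presented by arm overall, by SOC/PT, for SAEs, for fatal AEs and for each AESI. Adjudicated MACE and malignancies are also summarised by arm, and adjudication runs to the end of follow-up (Protocol 8.4.7). That stands. A reader might infer that no arm comparison of AEs after stopping treatment will exist, or that nothing about follow-up can be recovered from the tables. The documents support neither: the comparison exists in pooled form, and event totals can be subtracted. Only the separate subject counts and the rates are missing.

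A second defence is that the 33-day rule is stated openly with its reason, matches the visit window and treats both arms alike. That also stands. The documents give no ground for reading it as concealed or as favouring an arm. What remains is that it disagrees with Protocol 9.4.3.2 and is not declared where the SAP says changes will be.

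A third is that Protocol 9.5.4 leaves detail to the SAP. This does not reach the point, because removing one of two named periods is more than detail.

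For early discontinuers the SAP is in one respect wider than the protocol. It would be wrong to say that the protocol promised them more than 12 weeks of AE follow-up, since its period stops at + 16 weeks.

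**Conclusion.** The point holds in a limited form. The SAP omits a follow-up-period AE summary with exposure-adjusted rates that the protocol plans, and Section 6 says nothing has changed. The loss is follow-up subject counts by SOC/PT and follow-up rates, covering 79 days per completer under the SAP boundary (84 under the protocol's). The boundary difference is secondary: 5 of 84 days, equal in both arms, with no demonstrated effect on any conclusion. The day counts assume visits on their target days and dosing through Week 48. The primary efficacy analysis is not affected. This is a minor point, worth making because it is cheap to correct and the statement of no change is inaccurate as it stands.

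**What to change.** 1. **Preferred:** add to SAP 4.2.7.1 a post-treatment AE table by SOC/PT and treatment group, with counts and exposure-adjusted rates. A matching SAE table is optional. SAP 3.3.2 already defines time at risk generically, as time in the relevant period without the event. It needs only a start (the day after last dose + 33 days, if that boundary is kept) and an end (study completion, withdrawal, death or first post-treatment occurrence, whichever is earliest). State whether subjects who already had the term on-treatment stay in the denominator.
2. **Alternative:** if the summary is dropped on purpose, say so in SAP Section 6 with the reason.
3. **Either way:** reconcile the 4-week and 33-day boundaries, and the protocol's + 16-week cap with the SAP's uncapped period. Record the rule kept in Section 6; if it is 33 days, give the 28 + 5 derivation.

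Cost: one or two tables and a few sentences. No new data are needed, because AEs are already collected to the end of the study (Protocol 8.3.2).

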4.2.7.2 Laboratory data

All continuous laboratory variables will be summarised by absolute value at each visit by treatment group, together with the corresponding changes from baseline. These summaries will be produced for the on-study period as defined in Section 3.1.4. The summary statistics presented will be the minimum, 1st quartile, median, 3rd quartile, maximum, mean, and standard deviation (SD).

Central laboratory normal reference ranges will be used for the identification of individual clinically important abnormalities. A shift table will be produced for each laboratory variable to display low, normal, and high values. The shift tables will present baseline and maximum/minimum/last post-baseline values for each variable.

Shift plots showing each individual subject's laboratory value at baseline and at maximum/ minimum/ last value post-baseline will be produced for each continuous laboratory variable. If any laboratory variables show any unusual features (high or low values or a general shift in the data points) at other time points then shift plots of these data may be produced. The diagonal line of no change, and horizontal and vertical reference lines indicating the limits of the normal reference ranges, will also be displayed on the shift plots.

Both shift tables and shift plots will be produced using all data for the on-study period, as defined in Section 3.1.4.

The frequencies of clinically noteworthy values (using normal reference ranges) occurring during the study will also be given.

In order to identify potential Hy's Law cases, maximum post-baseline TBL will be plotted separately against both maximum post-baseline ALT and AST, expressed as multiples of ULN. These plots will be produced on a log scale, with reference lines included at 2xULN for TBL, and at 3xULN for both ALT and AST. These plots will be produced using all data for the on-study period.

For all subjects who meet the biochemical criteria for Hy's Law (potential Hy's Law cases), the relevant laboratory variables will be tabulated showing all visits for these subjects.

Subjects with elevated ALT or AST in addition to elevated TBL at any time may be explored further graphically using individual subject profile plots.

For urinalysis data, a shift table will be generated to present changes from baseline to maximum/last value post-baseline. All data for the on-study period will be used.

Any data outside the central laboratory reference ranges will be explicitly noted on the listings that are produced.

Microbiology data will be listed.

4.2.7.3 Vital signs

All vital signs variables will be summarised by absolute value at each visit by treatment group, together with the corresponding changes from baseline. These summaries will be produced for the on-study period. The summary statistics presented will be the minimum, 1st quartile, median, 3rd quartile, maximum, mean, and SD.

AZ-defined reference ranges (see Section 3.3.5) will be used for the identification of individual abnormalities. A shift table will be produced for each vital sign variable to display low, normal, and high values. The shift tables will present baseline and maximum/minimum/last post-baseline values for each variable.

Shift plots showing each individual subject's vital sign value at baseline and at maximum/minimum/last value post-baseline will be produced for each continuous vital sign variable.

Both shift tables and shift plots will be produced using all data for the on-study period.

Subjects who have treatment-emergent changes from baseline outside the pre-defined AZ clinically important change criteria in Section 3.3.5 will be presented. All data for the on-study period will be used.

4.2.7.4 Twelve lead electrocardiogram (ECGs)

A shift table will be produced for each ECG parameter to display normal, abnormal – not clinically significant, abnormal - clinically significant, and not done. The shift tables will present baseline and last observation post-baseline value.

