9.4.3 Calculation or Derivation of Safety Variables

9.4.3.1 Safety Variables

The following safety data will be collected: vital signs, physical examination, 12-lead ECG, hematology, clinical chemistry, urinalysis, and reported AEs.

Change from baseline (last measurement prior to first IP administration) to each post-treatment time point where scheduled assessments were made will be calculated for relevant measurements. AEs will be summarized by means of descriptive statistics and qualitative summaries.

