1. STUDY DETAILS

This is the statistical analysis plan (SAP) for study D5241C00001. The SAP describes the statistical analyses specified in the latest version of the clinical study protocol (CSP) in more detail; any changes to what is specified in the CSP will be described in Section 6.

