4.2.7.5 Smoking status

Smoking status changes will be summarised by treatment group and visit for subjects in the safety analysis set during on-study period. A shift table will be produced to display current, former smoker and missing. The shift tables will present baseline and last observation post-baseline value.

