6. CHANGE OF ANALYSIS FROM PROTOCOL

There are no changes of analysis from the protocol.

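### SAP 4.2.7.4 plans only a baseline-to-last ECG shift, although protocol 9.5.4 calls for ECG changes at each visit and noteworthy-value frequencies during the study, and SAP Section 6 declares no change

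*SAP*

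**What the plan says.** Protocol 9.5.4 (Safety Analyses) treats vital signs and ECGs together: "Changes in vital signs and ECGs will be examined at each visit and at endpoint". The sentence that follows reads: "Frequencies of clinically noteworthy values (defined in the SAP) occurring during the clinical study will be presented".

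SAP 4.2.7.4 is the only place in the SAP that plans an ECG output. It specifies a shift table with four categories (normal, abnormal but not clinically significant, abnormal and clinically significant, not done) and limits the time points: "clinically significant, and not done. The shift tables will present baseline and last observation post-baseline value". SAP 3.3.6 describes only how the overall evaluation is recorded.

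On departures from the protocol, SAP Section 1 says that "any changes to what is specified in the CSP will be described in Section 6". Section 6 says: "There are no changes of analysis from the protocol". The SAP amendment history lists no ECG change.

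The neighbouring safety sections are fuller. For laboratory data, SAP 4.2.7.2 adds to its by-visit summaries: "The frequencies of clinically noteworthy values (using normal reference ranges) occurring during the study will also be given". SAP 4.2.7.3 summarises vital signs by visit, with maximum and minimum shifts and a presentation of changes outside preset criteria. SAP 4.2.7.5 covers another categorical variable with a last-value shift, and still states: "Smoking status changes will be summarised by treatment group and visit for subjects in the safety analysis set during on-study period".

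**The concern.** The SAP keeps the endpoint part of the protocol's ECG analysis. It has no by-visit part, and nothing that counts noteworthy ECG findings over the study. The change is not declared.

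The gap matters because of protocol 8.3.7. That section says mandated ECG results will be summarised in the study report. It gives this as the reason for reporting an ECG deterioration as an adverse event only if it is serious or is the reason for stopping investigational product. Any associated sign or symptom is still reported. The adverse event route is therefore narrowed in reliance on the ECG summary, and the planned summary uses one post-baseline reading per subject.

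At stake is a comparison between arms of lesser, transient ECG findings. ECG is a named safety variable in both documents, and protocol Table 3 lists serious cardiac events as an important potential risk after a numerical imbalance in cardiac serious adverse events in a long-term extension study.

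**Working it through.** **Step 1: set the two documents side by side.**

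| Element | Protocol 9.5.4 | SAP for ECG | SAP for vital signs | SAP for laboratory data |
|---|---|---|---|---|
| Each visit | Yes, for vital signs and ECGs | None | By-visit summary | By-visit summary |
| Endpoint | Yes, for vital signs and ECGs | Shift to last value | Shift to last value | Shift to last value |
| Findings over the whole study | Noteworthy-value frequencies, to be defined in the SAP | None, and no definition | Max/min shifts and out-of-criteria changes | Max/min shifts and noteworthy-value frequencies |

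The visit-window rules in SAP 3.1.5 classify data for analyses presented by time point. They do not create an ECG analysis where none is specified.

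**Step 2: count the readings.** Protocol Table 2 schedules ECGs at Visits 3, 6, 9, 13 and 16, that is Weeks 0, 12, 24, 40 and 52, plus the discontinuation and exacerbation visits. A completer has four scheduled post-baseline ECGs. The shift table uses one of them, so 4 − 1 = 3 enter no planned summary by arm.

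**Step 3: follow one case.** A subject has a clinically significant ECG at Week 24, no symptoms, no seriousness criterion and no discontinuation. Week 52 is normal.
- Under protocol 8.3.7 it is not an adverse event, so it is absent from the tables in SAP 4.2.7.1.
- In the SAP 4.2.7.4 table the subject counts as normal.
- It may appear in a listing, but a listing does not compare arms.

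**Step 4: illustrate the size.** The documents give no ECG abnormality rate, so p and r below are assumptions.
- n = 169 per arm (planned size), all fully followed, four readings. ECGs at discontinuation and exacerbation visits are ignored.
- p = prevalence of a clinically significant ECG at each reading.
- r = probability that a finding present at one reading is still present at the next.
- With prevalence constant over time, the chance of a finding at the next reading when there is none now is q = p(1 − r)/(1 − p).
- Shown in the table = n × p.
- Affected at any time = n × [1 − (1 − p)(1 − q)³].
- Missed = the difference.

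Worked case, p = 1%, r = 0.5:
- q = 0.01 × 0.5/0.99 = 0.00505
- Any time = 169 × [1 − 0.99 × 0.99495³] = 169 × 0.02492 = 4.21
- Shown = 1.69
- Missed = 2.52

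Fully transient findings mean that readings are independent (r = p), so any time = n × [1 − (1 − p)⁴].

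| p | Shown per arm | Missed, all persist (r = 1) | Missed, half persist (r = 0.5) | Missed, fully transient |
|---|---|---|---|---|
| 0.5% | 0.84 | 0 | 1.26 | 2.51 |
| 1% | 1.69 | 0 | 2.52 | 4.97 |
| 2% | 3.38 | 0 | 5.02 | 9.74 |
| 5% | 8.45 | 0 | 12.34 | 22.90 |

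The definition of p matters. If 1% were the chance of a new finding at each reading and all findings persisted, the last-value table would itself show 169 × (1 − 0.99⁴) = 6.7 subjects.

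**Step 5: check the baseline of the one planned table.** SAP 3.1.2 takes the latest ECG before first dose. SAP 3.3.6 repeats protocol 9.4.3.5 and places baseline between Visit 1 and Visit 2. An ECG is also scheduled at Visit 3, so the two rules can select different readings.

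**The case against.** The strongest reply has four parts.

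**The protocol does not promise a count of clinically significant ECGs.** A reader might infer that it does. It speaks of noteworthy values and leaves the definition to the SAP. ECGs here carry a graded overall evaluation, with no numeric limits like those for vital signs. This stands: equating the two is a sensible inference and not protocol text. The SAP nevertheless supplies no other definition, so the delegated item is still open for ECGs.

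**Protocol 9.4.3.1 adds little.** It lists the ECG among the safety data and says that change from baseline "to each post-treatment time point where scheduled assessments were made will be calculated for relevant measurements". The limit to relevant measurements means it need not reach a categorical evaluation. This stands, and the point rests on 9.5.4.

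**Examining is looser than tabulating.** Section 9.5.4 leaves further detail to the SAP, and SAP 3.1.5 lets overall data be listed rather than analysed. This softens the charge without removing it. The SAP plans no by-visit ECG display of any kind, while vital signs, named in the same protocol sentence, have one.

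**The consequence is small.** Symptoms are captured as adverse events. Serious cardiac events are an event of special interest (SAP 8.1.6). Serious adverse events and adjudicated major cardiac events are summarised (SAP 4.2.7.1), and the monitoring committee reviews cardiovascular events during the trial. All of this stands and sets the limit of the point.

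**Conclusion.** The point holds as an undeclared reduction of the ECG analysis. The gap against the each-visit commitment in protocol 9.5.4 follows directly from the text. That the noteworthy-value sentence reaches clinically significant ECGs is a reasonable reading and is not explicit. Either way, the Section 6 statement is not accurate as it stands.

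The certain part of the size is that three of a completer's four scheduled post-baseline ECGs enter no planned summary by arm. The number of subjects missed is not known. At an assumed 1% prevalence it runs from 0 to about 5 per arm, depending wholly on persistence. The effect on the difference between arms cannot be estimated from the documents.

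Two stronger readings are not supported. A reader might infer that serious cardiac harm could go unseen, but serious events have their own definition, tables and adjudication. A reader might also take the illustrative counts as an expected loss, but they rest on assumed inputs and their range includes zero. The impact is confined to lesser, transient ECG findings, and no efficacy result changes. The SAP should be corrected, but the trial's conclusions do not depend on it.

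**What to change.** In SAP 4.2.7.4, keep the last-value shift and add, for the safety analysis set:

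1. Counts of each ECG category by scheduled visit and treatment group.
2. The number and percentage of subjects per arm with any post-baseline ECG graded abnormal and clinically significant over the on-study period, or a baseline-to-worst shift. State that this grade is the SAP's definition of a noteworthy ECG value.

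If the sponsor prefers the reduced analysis, Section 6 should say so and give the reason.

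Use one ECG baseline. The latest ECG before first dose (SAP 3.1.2) also agrees with the general rule in protocol 9.4.3.1. SAP 3.3.6 should then be corrected, and because protocol 9.4.3.5 says otherwise, Section 6 should record the choice.

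The cost is SAP wording and two extra outputs to programme and review, from data already collected. No protocol amendment is needed.
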